5.7 Tests (See Table 5.2 for test scheme.)

Each subject will be provided with all the materials needed for self-testing during the visit: one CONTOUR NEXT meter, one CONTOUR TV3 meter, a Microlet NEXT or similar lancing device, lancets, Contour NEXT test strips, V3 test strips, CONTOUR NEXT and CONTOUR TV3 UGs and QRGs. The subject will be given time to review the UG and QRG to learn how to use the system but no training will be provided.

The subject will wash his/her hands thoroughly with warm water and soap, rinse and dry well.

5.7.1 **Fingerstick Testing**

1. The subject will perform a fingerstick using the Microlet NEXT lancing device and test his/her blood on Meter 1. The study staff person will record the time and test result of the successful meter test on the appropriate form. For instructions on handling error codes and repeat testing, refer to protocol section 5.10 'Errors'.
2. Immediately, but at least within 5 minutes of the fingerstick self-test, the study staff person will lance the subject's finger (preferably the same hand as above) with a Tenderlett device in order to collect enough blood for testing on the YSI Analyzer (approx. 200–300 uL). The time of this Tenderlett lancing will be recorded.
3. If adequate blood is not obtained from the Tenderlett lancing, 2 additional Tenderlett lancements are allowed (total of up to 3 Tenderlett lancements). The blood is to be combined into one tube for YSI analysis.
4. The blood sample will be centrifuged as soon as possible after sample collection but not longer than 15 minutes after the meter test. The study staff person will record the time of centrifugation.
5. In order to reduce glycolysis of the plasma, it is recommended that the plasma be transferred from the microtainer tube to a micro/dispo tube or similar container, prior to analysis on the YSI Analyzer.
6. The plasma sample will be assayed on the YSI Analyzer: 1 sip = 1 result from black probe and 1 result from white probe. See 5.12.3 for details on testing of plasma samples.

7. Immediately following the subject plasma sample, a serum control close to the level of the subject plasma will be tested. (No re-calibration is required). The serum control test result should be within the range shown in Table 5.1. See 5.12.3 for details.
8. Additional details regarding processing of blood samples for the YSI Analyzer are found in Appendix B.
9. If the time from meter test to blood centrifugation exceeds 15 minutes, the test is considered non-evaluable. This will not be considered a protocol deviation. Times of meter tests and centrifugation will be recorded.

5.7.2 AST (palm) testing

1. Only proceed to AST testing if an adequate blood sample is obtained from Tenderlett lancing for YSI analysis.
2. The same meter and test strip lot used for fingerstick testing will be used for AST testing.
3. Immediately following Step 5.7.1, the subject will perform an AST (palm) stick using the lancing device (new lancet), preferably on the same hand as the fingerstick lancing, and test his/her blood on Meter 1.
4. If adequate blood is not obtained from the Microlet palm lancements for the meter test, up to 2 additional Microlet palm lancements are allowed (total of up to 3 AST palm lancements).
5. The time of the successful AST meter test will be recorded. The time interval between the blood centrifugation and the AST meter test should be as soon as possible, and within 15 minutes or less.
6. If the time from meter test to blood centrifugation exceeds 15 minutes, the test is considered non-evaluable. This will not be considered a protocol deviation. Times of meter tests and centrifugation will be recorded.

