5.7.3 Study Staff test

1. Immediately following the AST testing, the study staff person will perform a fingerstick lancing using the same Microlet lancing device (new lancet) on the subject, preferably on the same hand as the other fingerstick lancing.
2. The staff person will test the fingerstick blood using the same meter and test strip lot used by the subject.
3. The study staff will record the time of the meter test. The time interval between the blood centrifugation and the final staff meter test should be as soon as possible, and within 15 minutes or less.
4. If the time from meter test to blood centrifugation exceeds 15 minutes, the test is considered non-evaluable. This will not be considered a protocol deviation. Times of meter tests and centrifugation will be recorded.

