 - Centrifuge the whole blood immediately to separate the plasma from the red blood cells. Centrifugation must occur within 15 minutes of first meter blood test. Timing of all meter testing/centrifugation will be recorded on the appropriate CRF.
 - It is recommended that after centrifugation, the plasma is transferred from the microtainer tube to a micro/dispo tube or similar container. Ensure the container is labeled and the cap is secured.
 - The capped plasma sample may be kept at room temperature for up to 4 hours before testing.

2. If testing on the YSI Analyzer is not completed within 4 hours of sample collection, the plasma should be refrigerated for up to 24 hours, after which it should be frozen until the sample is tested.
3. Shipment of samples to Ascensia for glucose determinations may be recommended if YSI Analyzers do not meet the accuracy guidelines for the Ascensia traceability control sera. Arrangements will be made to ship the samples with dry ice via prepaid express mail should it become necessary.
4. Glucose values of the YSI replicates (controls and plasma) should be within 4 mg/dL or 4% of each other; if not, an additional assay should be run.
5. Insufficient (or suspected to be insufficient) samples, missing samples, and other sample issues should be recorded in the CRF and on the YSI printout as appropriate. If a sample is hemolyzed, record in the CRF.

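### Palm and staff results qualify by time to centrifugation, not time from the comparator draw, so an evaluable pair may be up to 25–30 minutes apart

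*Combined protocol and SAP*

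**What the plan says.** For each meter, one Tenderlett capillary sample supplies the YSI comparator for the subject's fingerstick, the subject's palm test and the staff fingerstick (Sections 3.0 and 5.9.1). The steps run in the order self-test, Tenderlett draw, palm test, staff test (Table 5.2, steps 1–4).

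- **Draw.** Section 5.7.1(2) places it "Immediately, but at least within 5 minutes of the fingerstick self-test" and adds: "The time of this Tenderlett lancing will be recorded".
- **Centrifugation.** Under 5.7.1(4) the sample is to be "centrifuged as soon as possible after sample collection but not longer than 15 minutes after the meter test". Appendix B repeats the limit: "Centrifugation must occur within 15 minutes of first meter blood test".
- **Palm test.** 5.7.2(5): "The time interval between the blood centrifugation and the AST meter test should be as soon as possible, and within 15 minutes or less".
- **Staff test.** 5.7.3(3): "The time interval between the blood centrifugation and the final staff meter test should be as soon as possible", with the same 15-minute bound.
- **Evaluability.** 5.7.2(6), 5.7.3(4) and the general rule in 5.9.7 all use the same test: "If the time from meter test to blood centrifugation exceeds 15 minutes, the test is considered non-evaluable".

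The Tenderlett time is collected, but no evaluability rule uses it.

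**The concern.** Time to centrifugation limits glycolysis in the tube, which is a sound purpose. For the venous test it fits the design, because meter and YSI are fed from one tube. The palm and staff tests differ: the blood on the strip leaves the body after the comparator blood did. Any change in the subject's glucose over that interval enters the meter-minus-YSI difference, and the rule does not bound that interval.

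Four pass counts use these pairs. In Table 11.1 they are 333 of 350 for palm in all subjects (2.2.1), 300 of 315 for palm in subjects with diabetes (2.3.2), and 327 of 350 and 294 of 315 for the staff test (2.4.2). The same rule also decides which results count towards the required 350 evaluable palm results.

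**Working it through.** **Inputs.** Let T0 be the fingerstick self-test, with times in minutes.

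- Draw at T0 + d, with 0 ≤ d ≤ 5 (5.7.1(2)).
- Centrifugation at T0 + c, with d ≤ c ≤ 15 (5.7.1(4), Appendix B).
- Palm or staff test at T0 + m, with |m − c| ≤ 15 (5.7.2(5)–(6), 5.7.3(3)–(4)).

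**Longest permitted gap.** The draw-to-test gap is m − d. Its maximum is 15 + 15 − d = 30 − d, which is 30 minutes if the draw is at T0 and 25 minutes if it is at T0 + 5. The fingerstick self-test is at most 5 minutes from the same draw.

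**Effect of the spin time.** Take a draw at T0 and a palm test at T0 + 20.

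- Spun at T0 + 4: 20 − 4 = 16 minutes, non-evaluable.
- Spun at T0 + 12: 20 − 12 = 8 minutes, evaluable.

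The two blood samples are 20 minutes apart in both cases. The prompt spin loses the pair and the slow one saves it.

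**Late spin.** 5.7.1(9) voids only the test whose own interval is exceeded. If the tube were spun at T0 + 20, outside the Appendix B limit, the self-test would be lost. A palm test at T0 + 35 would still meet its own rule, 35 minutes after a draw at T0.

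**The plan's own figure.** Section 11.1 gives about a 95% chance of passing with n = 350, Xc = 333 and P0 = 96.65%, and Table 11.1 applies this to 2.2.1. The exact binomial P(X ≥ 333 | 350, 0.9665) is 0.950, and the chance of failing at 92.81% is 0.9495. Both reproduce.

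**Size of drift.** The documents give no drift rates; those below are assumptions. Drift = rate × gap.

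| Rate (mg/dL/min) | 5 min | 15 min | 25 min | 30 min | 30 min at 150 mg/dL |
|---|---|---|---|---|---|
| 0.5 | 2.5 | 7.5 | 12.5 | 15 | 10% |
| 1 | 5 | 15 | 25 | 30 | 20% |

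For 2.3.2 and 2.4.2 the allowance is ±15 mg/dL below 100 mg/dL and ±15% from there up. For 2.2.1 it is ±15% and ±20% at all concentrations.

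**Illustration for 333 of 350.** Suppose a share f of pairs is accurate with probability q, and the rest with 0.9665. Then p = (1 − f) × 0.9665 + f × q. With f = 0.05 and q = 0.80, p = 0.9182 + 0.0400 = 0.9582. Both f and q are assumptions.

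| f | Pass probability, q = 0.90 | Pass probability, q = 0.80 |
|---|---|---|
| 2% | 0.933 | 0.900 |
| 5% | 0.901 | 0.783 |
| 10% | 0.828 | 0.510 |

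**The case against.** Reaching 30 minutes means stretching several instructions at once. Section 3.0 has the palm stick follow directly on the Tenderlett lancing, and 5.7.3(1) has the staff test follow directly on the palm test. Section 5.7.1(4) and Appendix B call for a prompt spin. A palm test done before a timely spin is necessarily within 15 minutes of the draw. Section 5.9.13 also restricts eating and medication during the sequence and voids results obtained afterwards. All of this stands, and most gaps should be well below the maximum.

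It does not close the point. The promptness instructions carry no draw-to-test limit in minutes and are not evaluability criteria. Section 5.9.13 does not deal with a meal or dose taken before testing. Up to three palm lancings (5.7.2(4)) and up to three attempts after error codes (5.10.1) can come before the staff test. The sequence is not uniform either: 5.7.2(3) places the palm test after the whole of 5.7.1, which includes centrifugation, whereas Section 3.0 places it straight after lancing.

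Three stronger readings are tempting, and the documents support none of them.

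- A reader might infer that evaluable pairs will typically be about 30 minutes apart. The documents give no expected gap or frequency.
- A reader might infer that the primary accuracy result is compromised. It is not, because its comparator draw must follow within 5 minutes.
- A reader might infer that the rule helps an inaccurate meter to pass. Drift can occasionally offset meter error, but it mainly adds discrepancy, so the main risk is a failed objective that does not reflect the meter.

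**Conclusion.** The point holds as a gap in the evaluability rule for palm and staff tests. With all stated windows met, a pair up to 25–30 minutes apart still counts, and the permitted window lengthens as centrifugation is delayed. The gap follows from the text alone. Its effect on accuracy does not: the 15–30 mg/dL figure needs a sustained drift of 0.5–1 mg/dL/min over the full worst-case gap, and the lower pass probabilities need an assumed share of affected pairs with an assumed accuracy. Only secondary objectives are touched (2.2.1, 2.3.2 and 2.4.2, the last being internal), together with the palm evaluable count. The change is worth making because it is cheap and protects those objectives from a timing artefact.

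**What to change.** For palm and staff tests only, amend 5.7.2(5)–(6), 5.7.3(3)–(4) and Table 5.2 steps 3–4, with a matching exception in 5.9.7:

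1. Base evaluability on the time from the recorded Tenderlett lancing to the meter test. Fifteen minutes is an example; the documents set no draw-to-test limit, so the sponsor should choose and justify one.
2. State which lancing time counts when blood from up to three Tenderlett lancings is pooled (5.7.1(3)).
3. Leave unchanged the requirement to centrifuge within 15 minutes of the fingerstick self-test (5.7.1(4), Appendix B), and require it also for the palm and staff pairs that use the sample. A limit of 15 minutes from lancing instead would allow 5 + 15 = 20 minutes after the self-test and conflict with the existing one.
4. Leave the fingerstick and venous rules as they are.

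If the present rule is kept for the main count, pre-specify pass counts for 2.2.1, 2.3.2 and 2.4.2 under the draw-anchored rule as well.

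The cost is wording and one derived time variable, since lancing, centrifugation and meter times are already recorded. Some late pairs would become non-evaluable. The documents do not show how many, so a few more subjects may be needed to reach 350 evaluable palm results.

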5.7.3 Study Staff test

1. Immediately following the AST testing, the study staff person will perform a fingerstick lancing using the same Microlet lancing device (new lancet) on the subject, preferably on the same hand as the other fingerstick lancing.
2. The staff person will test the fingerstick blood using the same meter and test strip lot used by the subject.
3. The study staff will record the time of the meter test. The time interval between the blood centrifugation and the final staff meter test should be as soon as possible, and within 15 minutes or less.
4. If the time from meter test to blood centrifugation exceeds 15 minutes, the test is considered non-evaluable. This will not be considered a protocol deviation. Times of meter tests and centrifugation will be recorded.

5.8 Venous Blood Testing by Study Staff (Only subjects with diabetes)

- 5.8.1 The venipuncture and subsequent test may be performed at any time during the subject visit.

- 5.8.2 A venipuncture will be performed by a trained site phlebotomist. The subject's blood will be collected into one 4 mL heparin-coated Vacutainer tube.
- 5.8.3 The study staff person will place one drop of venous blood onto Parafilm[®], then immediately perform one test with the same lot of test strips and the same meter used for capillary tests. Record the time of the successful venous meter test.
- 5.8.4 Refer to Section 5.10 for information on handling error codes and repeat testing.
- 5.8.5 The venous blood will be centrifuged as soon as possible after the meter test (within 15 minutes or less). Record the centrifugation time. If the time from meter test to blood centrifugation exceeds 15 minutes, the test is considered non-evaluable. This will not be considered a protocol deviation. Times of meter tests and centrifugation will be recorded.
- 5.8.6 Additional details regarding processing of blood samples for the YSI Analyzer are found in Appendix B.
- 5.8.7 The venous plasma sample will be assayed on the YSI Analyzer: 1 sip = 1 result from black probe and 1 result from white probe. See 5.12.3 for details on testing of plasma samples.
- 5.8.8 Up to three venipuncture attempts are allowed per subject, if subject and study staff agree, in order to obtain sufficient venous blood. If the venipuncture is ultimately unsuccessful, this will be recorded and will not be considered a protocol deviation.

5.9 **General**

- 5.9.1 All fingerstick and AST meter test results will be compared to the capillary YSI laboratory results.
- 5.9.2 All venous blood meter test results will be compared to the venous blood YSI laboratory results.
- 5.9.3 If adequate blood is not obtained from the subject or staff Microlet lancings, up to 2 additional lancings are allowed in each case (up to a total of 6 fingertip Microlet lancings).
- 5.9.4 If adequate blood is not obtained from the staff Tenderlett lancings, up to 2 additional lancings are allowed in each case (up to a total of 3 fingertip Tenderlett lancings).
- 5.9.5 If adequate blood is not obtained from the Microlet AST palm lancings, up to 2 additional palm lancings are allowed (total of up to 3 AST palm Microlet lancings).
- 5.9.6 If adequate blood is not obtained from the first venipuncture attempt, up to 2 additional attempts are allowed if subject and study staff agree (total of up to 3 venipuncture attempts).
- 5.9.7 **If the time from meter test to blood centrifugation exceeds 15 minutes, the test is considered non-evaluable.** This will not be considered a protocol deviation. Times of meter tests and centrifugation will be recorded.
- 5.9.8 Hand warmers may be used throughout the testing to increase blood flow.
- 5.9.9 It is preferred that all fingerstick and AST lancings are from the same hand if possible, for each meter.
- 5.9.10 Study staff will record all meter results on the appropriate form. If meters have turned off, meter memory will be reviewed and the results will be obtained from meter memory.

- 5.9.11 Study staff will record every instance of second chance sampling by checking the box provided on the CRF.
- 5.9.12 Study staff will record in the comments section of the meter testing form, any obvious testing errors by the subject or staff as appropriate for staff tests, and any abnormalities observed in the testing procedure or BGMS.
- 5.9.13 Note that once the fingerstick testing is started in 5.7.1, the subject should not eat, or use medications until the capillary/AST testing is completed in 5.7.2 to avoid changing glucose levels. The subject can eat/take medicines at any time to avoid or treat hypoglycemia or hyperglycemia. If the subject eats or takes medications, results obtained after eating or medicating will be non-evaluable.

5.10 Errors

- 5.10.1 If the meter reports an error code, the instructions shown in the UG should be followed. Re-testing is recommended (per the UG). No more than a total of 3 attempts are allowed.
- 5.10.2 If the subject feels that he/she made an error while testing, without any prompting from the study staff, he/she will repeat the test. The reason for the repeated test will be documented in the comments section of the form.
- 5.10.3 If the study staff feels that he/she made an error while performing staff fingerstick or venous testing, he/she will repeat the test. The reason for the repeated test will be documented in the comments section of the form.
- 5.10.4 The study staff will record all non-numeric codes - QNS (Quantity not sufficient), NO (Not obtainable), and meter error codes as appropriate for the meter tests.

5.11 Hematocrit

Two hematocrit tubes will be filled with either the subject's venous or capillary blood, and then centrifuged. The hematocrit will be measured from only one tube; the second tube will be collected as a backup in case the first tube is not measureable (i.e., tube spun out, broken tube, clay seal compromised, etc.). Subject hematocrit measurement should be within 0-70% in order for the subject BG results to be considered evaluable.

Note: Microhematocrit tubes with anticoagulant will be used for capillary blood hematocrit measurements collected directly off the fingertip and microhematocrit tubes without anticoagulant will be used for venous blood.

Additional details regarding hematocrit measurements are found in Appendix C.

5.12 YSI Glucose Analyzer

5.12.1 YSI Analyzer Operation and Control Tests

The YSI Glucose Analyzer will be maintained and operated according to the instructions in the manufacturer's operating manual.

Before the study begins, the YSI will be set up and appropriate maintenance will be performed. The YSI clock will be set to 24 hour format using an accurate time device, such as site central clock or atomic clock.

A set of four glucose control sera³ that have been assayed by a method traceable to one proposed for use as a national glucose reference method developed through the combined efforts of the Center for Disease Control, the National Bureau of Standards, the American Association for Clinical Chemistry, and the FDA will be provided by Ascensia and used to verify the accuracy of the YSI Glucose Analyzer⁴. These controls will be run for pre-study and daily control tests, and will be within the lower and upper limits of the target levels noted in Table 5.1. The procedure for proper thawing and handling of the serum controls is found in Attachment 1.

Table 5.1: YSI serum control target values and limits, mg/dL

LOT#	LEVEL	TARGET	Lower Limit	Upper Limit
7AP204	2	49.1	46.6	51.6
7AP304	3	96.8	92.0	101.6
7AP404	4	193.5	183.8	203.2
7AP505	5	390.2	370.7	409.7

5.12.2 Pre Study and Daily Control Tests

These four glucose control sera will be used to verify the accuracy of each YSI analyzer before the study begins (Pre-study testing). Six (6) pre-study runs will be performed on each YSI that will be used in the trial: 2 runs per day for 3 days. The Ascensia Study Manager or designee will review the YSI pre-study glucose control data before the study begins.

The daily controls will be tested: 1 sip = 1 result from white probe and 1 result from black probe. Any YSI used on a given day to test subject blood samples will be monitored by assaying the 4 glucose controls at the beginning of the day. The YSI will be calibrated before each serum control sample is tested. The sequence of testing will be:

1. Calibrate the YSI
2. Test Control 2 (1 sip)
3. Calibrate
4. Test Control 3 (1 sip)
5. Calibrate
6. Test Control 4 (1 sip)
7. Calibrate
8. Test Control 5 (1 sip)

³ Caution: The glucose traceability controls are human serum-based and must be handled using universal precautions.

⁴ Neese J, Duncan P, Bayse D, *et al.* Development and evaluation of a hexokinase/glucose-6-phosphate dehydrogenase procedure for use as a national glucose reference method. HEW Publication No. (CDC) 77-8330. 1976. Atlanta, Centers for Disease Control.

Site staff will keep a maintenance log for each YSI, including daily operational checks, maintenance and membrane changes. A full set of serum controls should also be tested after YSI parts are changed (such as buffers, probes, or membranes).

5.12.3 Testing of Subject Plasma Samples

The subject plasma samples (capillary and venous) will be tested using 1 sip per test (=2 results, 1 from white and 1 from black probe) with calibration of the YSI before the first sip. A serum control (1 sip) will be tested after each subject plasma sample to verify the YSI Analyzer has remained in control during the plasma sample test. The control with target value close to the concentration of the subject plasma sample will be tested. The average of the black and white probe results will be verified to be within the ranges shown in Table 5.1.

If the control result is out of range, the YSI will be recalibrated and the control sample will be retested. If the control result is now within the appropriate range (Table 5.1), the control sample is confirmed as appropriate for use. The YSI analyzer will then be re-calibrated, the plasma will be re-tested, and the control will be tested per the protocol's plasma testing procedure already described.

If the control result is not within the appropriate range after the plasma sample has been tested twice, the results for this subject sample will be non-evaluable.

The sequence of testing for each subject sample will be:

1. Calibrate the YSI
2. Test plasma sample (1 sip)
3. Test control (1 sip)
4. Verify control result (mean of black and white probe results) is within limits in Table 5.1. If it is, stop and record result.
5. If not, repeat Steps 1, 3 and 4 to verify control sample is satisfactory for use.
6. When control result is shown to be within range in Table 5.1, repeat Steps 1-3.

If the control is again outside the limits, the results for this subject sample are non-evaluable.

Glucose values of the YSI replicates (both controls and plasma) should be within 4 mg/dL or 4% of each other (i.e. 4 mg/dL for values < 100 mg/dL and 4% for values \geq 100 mg/dL). If they are not, an additional assay should be run.

